### **2.1.9. Enlite Serter (MMT-7510) – FDA approval P120010**

The Enlite Serter is an insertion device used to ensure correct placement of the Medtronic MiniMed Enlite Glucose Sensor. The Serter injects the sensor into the insertion site when the button is released.

### **2.1.10. One-press Serter (MMT-7512) – FDA approval P120010/S070 and P150001**

The One-press Serter is an insertion device used to ensure correct placement of th Medtronic MiniMed® Enlite® Glucose Sensor. The serter injects the sensor into the insertion site when the button is released.

### **2.1.11. CareLink USB (MMT-7305) - FDA approval K070438**

The Medtronic CareLink USB (510 (k) clearance number K070438) is indicated for use commercially by patients at home and for clinicians in a medical office setting as a means of facilitating communication between Medtronic diabetes therapy management devices that use Paradigm-compatible RF telemetry and

a personal computer that uses data management application software. The CareLink USB device will enable data from the Medtronic MiniMed 530G to be uploaded to CareLink Clinical.

### **2.1.12. CONTOUR® NEXT LINK Blood Glucose Meter (HMS-9740) – FDA approval K110894**

The Contour NEXT LINK RF enabled BG Meter measures a subject's capillary blood glucose level, which is then used to calibrate the pump. The Medtronic MiniMed 530G pump uses the calibration point in the real-time algorithm which calculates the sensor glucose values that are displayed to the subject. In a normal setting, the result of the SMBG reading is transmitted to the pump via radiofrequency (RF) and can be stored in its memory as a glucose calibration point. The pump asks the user every time if the user wants to use the linked meter BG for calibration. If accepted, the glucose value will be stored in the pump's memory as a calibration point.

### **2.1.13. CONTOUR NEXT Test Strips (HMS-7309) and CONTOUR NEXT Control Solution (HMS-7314)**

The CONTOUR NEXT blood glucose test strips and CONTOUR NEXT Control Solutions will be used in conjunction with the CONTOUR NEXT LINK Blood Glucose Meter. These may be provided between study visits to subjects who are unable to adhere to CGM or CONTOUR NEXT LINK RF enabled meter and supply study requirements due to change in insurance coverage or financial status.

### **2.1.14. MICROLET® lancing device (HMS-6606) and MICROLET lancet (HMS-6586)**

The MICROLET lancing device is used to puncture the skin. The MICROLET lancets are coated with silicone for easier, gentler testing by reducing the surface friction of the needle.

## **3. Purpose of the Study**

The purpose of the study is to provide ongoing surveillance of the TS feature with a sensor augmented pump system over a 12 month period.

## **4. Objective and Hypothesis**

### **4.1. Study Objective**

The study objective is to demonstrate that home use of Threshold Suspend (TS) is not associated with glycemic deterioration. This objective will be demonstrated in several ways using two sub-studies:

- 1) Sub-study 1: Multi-Center Trial
  - Comparison of A1C measurement from baseline to end of study in the CEP266 study population
- 2) Sub-study 2: Commercial Data Evaluation
  - CareLink® data from the commercial MiniMed 530G users
  - Summary of supplementary data on hospitalized patients using the 530G system; taken from Medical Device Reporting (MDR)
  - Review of published data on the TS feature
  - Review of unpublished data on the TS feature, as available

## 5. Study Design

The evaluation of Threshold Suspend(TS) feature is conducted by two sub-studies: 1) Commercial Data Evaluation; 2) Prospective Multi-Center Trial.

### 5.1. Multi-Center Trial

The Multi-center trial was initiated to observe the Threshold Suspend (TS) feature with a sensor-augmented insulin pump (Medtronic MiniMed® 530G insulin pump) in patients 16 and older with insulin requiring diabetes over a period of one year.

In addition, additional data from commercial use will be analyzed/summarized to support the Multi-center trial as the enrolled population is lower (N=426) than the anticipated N=1000 subjects.

### 5.2. Commercial Data Evaluation

Additional dataset:

- CareLink® data from the commercial MiniMed 530G users
- Summary of supplementary data on hospitalized patients using the 530G system; taken from Medical Device Reporting (MDR)
- Review of published data on the TS feature
- Review of unpublished data on the TS feature, as available

#### 5.2.1. CareLink® data from the commercial MiniMed 530G users

Please refer to Statistical Section 7 for analysis.

#### 5.2.2. Summary Of Supplementary Data On Hospitalized Patients Using The 530G System; Taken From MDR

- Total number of uploaded data from pumps which also have MDR data
- Total number of hospitalizations for high blood glucose will be provided regardless of whether they were felt to be device related or not
- Summary of hospitalizations for high blood glucose which are device related will be provided including number of events and summary of causes
- Summary of hospitalizations for high blood glucose which are **NOT** device related will be provided including number of events and summary of causes

#### 5.2.3. Review Of Published Data On The TS Feature

A review and summary of the published scientific literature on the use of TS will be provided. Inclusion of “low glucose suspend” which is another term for threshold will be included. Detailed rationale and discussion on similarities and differences of low glucose suspend with Veo insulin pump versus 530G insulin pump and TS will be provided.

- a. Search date
- b. Period covered by the Search (e.g. There were no date limitations applied during search)
- c. Search engine utilized for medical review of literature will be provided Resources will include but not limited to:
  - i. <http://handbook.cochrane.org/>
  - ii. <http://prisma-statement.org/PRISMAStatement/PRISMAStatement.aspx>
  - iii. <http://prisma-statement.org/documents/PRISMA%202009%20flow%20diagram.pdf>
- d. Search medium used (e.g. online)

- e. Key terms used in search engine will be provided including brand names and Model numbers (e.g. TS, low glucose suspend, 530G insulin pump)
- f. Total number of articles/citations found in entire search will be provided
- g. Total number of articles/citations used in summary will be provided with rationale for selection criteria used to choose articles for full review (e.g. rationale for exclusion of articles if applicable)
- h. Summary of data and findings will include:
  - i. Title of study
  - ii. Device studied
  - iii. Population studied
  - iv. Number of subjects
  - v. Study Design
  - vi. Efficacy endpoints/results
  - vii. Safety which will include but not limited to adverse events or any device performance issues noted
  - viii. Reference of study
  - ix. Publication type
- i. Summary of this review with attention to Safety results will be provided and include a discussion on the limitations from this data. Conclusion will include risk benefit statement and justification of this statement based on these findings.

#### **5.2.4. Review Of Un-Published Data On The TS Feature, as Available**

The limitation of a review for only published data is that it excludes unpublished data which may have critical safety information. For example, there could be a selection bias to only publish data which is favorable on the use of the TS feature. Therefore, a review and summary of the unpublished data on the use of TS will also be provided if available. Inclusion of "low glucose suspend" which is another term used for TS will be performed.

- a. Medtronic sponsored studies (i.e. Investigator initiated grants or health care database analyses)
- b. Key terms used in search will be provided including brand names and Model numbers (e.g. TS, low glucose suspend, 530G insulin pump)
  - i. Characterization of how this search was performed will be provided
  - ii. Number of studies where devices using an automated TS provided by MDT as an investigator initiated grant will be summarized.
  - iii. Number of studies where investigator was able to be contacted on above studies to obtain unpublished data will be provided
  - iv. Number of studies where investigator was able to provided unpublished data will be provided
  - v. Summary of unpublished data and findings will include:
    - 1. Title of study
    - 2. Device studied
    - 3. Population studied
    - 4. Number of subjects
    - 5. Study Design
    - 6. Efficacy endpoints/results
    - 7. Safety which will include but not limited to adverse events or any device performance issues noted
  - vi. Summary of this review will provided if data is available and will include a discussion on the limitations from this data and attention to Safety results
- c. Non-Medtronic sponsored studies
  - i. Search in Clintrials.gov database for studies
  - ii. Search date
  - iii. Period covered by the Search (i.e., There were no date limitations applied during search)
  - iv. Key terms used in search engine will be provided including brand names and Model numbers (i.e., TS, low glucose suspend, 530G insulin pump)

- v. Characterization of how this search was performed will be provided
- vi. Number of studies where devices using an automated TS will be summarized.
- vii. Number of studies where investigator was able to be contacted on above studies to obtain unpublished data will be provided
- viii. Number of studies where investigator was able to provided unpublished data will be provided
- ix. Summary of unpublished data and findings will include:
  1. Title of study
  2. Device studied
  3. Population studied
  4. Number of subjects
  5. Study Design
  6. Efficacy endpoints/results
  7. Safety which will include but not limited to adverse events or any device performance issues noted
- x. Summary of this review will provided if data is available and will include a discussion on the limitations from this data and attention to Safety results. Conclusion will include risk benefit statement and justification of this statement based on these findings.

## 6. Study Population of Multi-Center Trial

### 6.1. Number of Subjects and CEP266 Study Population

A total of 426 subjects have been enrolled in the study.

40 Investigational centers were activated across the United States. Selection was based on Investigator's experience and qualifications, availability of sufficient resources to carry out the required study procedures and the investigator's ability to recruit subjects into the study.

Subjects will be grouped by baseline demographics: Baseline A1C, age, race, ethnicity, body mass index (BMI), gender, diabetes classification, duration of diabetes, hypoglycemic awareness and transition group. Sponsor will oversee distribution of subjects across study sites.

Summary of data will include the following baseline demographic categories:

- **Baseline A1C**
  - A1C less than 7.0%
  - A1C between 7.0% to 9.0%
  - A1C greater than 9.0%
- **Age Groups**
  - Adults age 22-and older
  - Adolescents age 16-21
- **Ethnicity**
  - Hispanic/Latino
  - Non-Hispanic/Non-Latino
  - Subject refused
- **Race**
  - American Indian/Alaska Native
  - Black/African-American

- White - anticipated maximum less than 80%
- Native Hawaiian/Other Pacific Islander
- Asian
- Other
- Subject refused
- **BMI according to WHO criteria [World Health Organization, 2011]:**
  - Underweight subjects (BMI less than 18.5 kg/m^2)
  - Normal weight subjects (BMI 18.5 to 24.99 kg/m^2)
  - Overweight subjects (BMI 25.00 to 29.99 kg/m^2)
  - Obese subjects (BMI 30.00 to 39.99 kg/m^2)
  - Morbidly obese subjects (BMI greater than or equal to 40 kg/m^2)
- **Gender**
  - Male
  - Female
- **Diabetes Classification**
  - Diabetes type 1
  - Diabetes type 2
  - Other diagnosis of Diabetes
- **Duration of diabetes**
  - Duration of diabetes less than 20 years
  - Duration of diabetes greater than or equal to 20 years
- **Hypoglycemic awareness**
  - Patients with intact hypoglycemic awareness
  - Patients who have impaired hypoglycemic awareness

- **Transition Groups**

The “transition” to the 530G system is based on the first time the TS (threshold suspend) feature is turned ON, outside/excluding pump training.

- Naïve: Subjects who have been exposed to the 530G pump therapy with the TS feature ON for 7 days or less prior to screening.
- Non-Naïve: Subjects who have been exposed to the 530G pump therapy with the TS feature ON for 8 to 365 days prior to screening.

## 6.2. Study Schedule / Duration

Each subject’s participation in the study will be comprised of 6 scheduled office visits over approximately 12 months. The entire study is expected to be completed within approximately 60 months from approval of the study protocol and the study device.

### **6.3. Inclusion Criteria for CEP 266 Study population**

1. Subject is age 16 or older at time of screening
2. Subject has been diagnosed with diabetes mellitus for at least one year prior to screening.
3. Subject is currently on pump therapy.
4. Subject is transitioning to the 530G insulin pump system with the TS feature turned ON.
5. Subject is willing to complete all study related activities
6. Subject is willing to upload data every 21 days from the study pump
7. Subject must have Internet access and access to a computer system that meets the requirements for uploading the pumps. This may include use of family or friend's computer system with Internet access.
8. Subject is able (by insurance or financial means) to cover the initial investment and ongoing cost of the 530G insulin pump and consumables, CGM, CONTOUR NEXT LINK RF enabled meter and supplies for the length of the study- 1 year.

### **6.4. Exclusion Criteria for CEP 266 Study population**

1. Subject is actively participating in an investigational study (drug or device) wherein he/she has received treatment from an investigational study drug or investigational study devices in the last 2 weeks.
2. Subject is a woman of child-bearing potential who has a positive pregnancy test at screening or plans to become pregnant during the course of the study
3. Subject is being treated for hyperthyroidism at time of screening
4. Subject has an abnormality ( $>1.8\text{mg/dL}$ ) in creatinine at time of screening visit
5. Subject has an abnormality (out of reference range) in thyroid-stimulating hormone (TSH) at time of screening visit. If TSH is out of range, Free T3 and Free T4 will be tested. Subject may be included with TSH out of range as long as Free T3 and Free T4 are in normal reference range.
6. Subject has taken any oral, injectable, or IV steroids within 8 weeks from time of screening visit, or plans to take any oral, injectable, or IV steroids during the course of the study
7. Subject is currently abusing illicit drugs
8. Subject is currently abusing prescription drugs
9. Subject is currently abusing alcohol
10. Subject has sickle cell disease or hemoglobinopathy
11. Subject has received red blood cell transfusion or erythropoietin within 3 months prior to time of screening or plans to receive red blood cell transfusion or erythropoietin over the course of study participation
12. Subject diagnosed with current eating disorder such as anorexia or bulimia
13. Subject has been diagnosed with chronic kidney disease that results in chronic anemia
14. Subject is on dialysis

## 7. Statistical Methods and Data Analysis

### 7.1. Multi-Center Trial

#### 7.1.1. Sample Size Calculation

##### 7.1.1.1. Sample Size for Primary Endpoint

The overall mean change in A1C from baseline to the end of study will be estimated and compared by a non-inferiority test with an A1C margin of 0.4% and a significance level of 0.025 (one-sided) with the CEP 266 study population. The null hypothesis will be rejected if the one-sided 97.5% upper confidence limit of the mean change in A1C is less than 0.4%

The hypothesis is mathematically expressed as:

Ho:  $\mu \geq 0.4\%$

Ha:  $\mu < 0.4\%$

Where 0.4% is the pre-specified non-inferiority margin,  $\mu$  is the mean of change in A1C (%).

Assuming the mean of change in A1C from baseline to the 12-month follow-up visit is zero, the standard deviation of change in A1C is 1%, SAS power and sample size calculator shows that a total of 100 subjects will provide over 95% power to detect the non-inferiority with a margin of 0.4% and with one-sided type I error of 0.025.

##### 7.1.1.2. Sample size for Adverse Event

Based on previous STAR3 IDE study (G060159), the serious adverse event rate for DKA and severe hypoglycemia was 14.79% (1.27% for DKA and 13.52% for severe hypoglycemia). Assuming a one year serious adverse event rate for DKA and severe hypoglycemia of 14.5%, a sample size of 480 would produce a one-sided 95% upper confidence limit around 17.5%. The actual one-sided 95% upper confidence limit for DKA incidence rate and severe hypoglycemia incidence rate will also be report separately.

#### 7.1.2. Study Populations

##### 7.1.2.1. Intention to Treat (ITT) Population

The Intention to Treat (ITT) population will include all enrolled subjects.

##### 7.1.2.2. Completed Case (CC) Populatio

The Completed Cases (CC) population is all subjects who complete the trial.

##### 7.1.2.3. Efficacy Population

The primary efficacy analysis will be performed on the CC population.

##### 7.1.2.4. Safety Population

The Safety Population will be the ITT population (include all enrolled subjects).

#### 7.1.3. Analysis of Primary Endpoint for CEP 266 Study Population

##### 7.1.3.1. Primary Efficacy Analysis

A mixed effects model will be used to produce the estimate and confidence interval of the overall mean change in A1C while accounting for inter-site variability: The 97.5% upper confidence interval of A1C will be calculated and compared to the 0.4% non-inferiority margin with the CEP 266 study population. As for endpoint analysis, the proposed mixed effects model using all A1C

measurements has more power than the model only using Change in A1C from baseline to one-year visit.

$$Y_{ij} = X_{ij}\beta + B_i + B_{ij} + \varepsilon_{ij}$$

where

$Y_{ij} = (Y_{ij1}, \dots, Y_{ij5})'$  is the A1C measurement vector for the  $j$ th subject in the  $i$ th site;

$$= \begin{pmatrix} 1 & 0 & 0 & 0 & 0 \\ 1 & 1 & 0 & 0 & 0 \\ 1 & 0 & 1 & 0 & 0 \\ 1 & 0 & 0 & 1 & 0 \\ 1 & 0 & 0 & 0 & 1 \end{pmatrix}$$

is a the covariate vector for the  $j$ th subject in the  $i$ th site;

$$\beta = \begin{pmatrix} \beta_0 \\ \beta_1 \\ \beta_2 \\ \beta_3 \\ \beta_4 \end{pmatrix}$$

is the coefficient vector,  $\beta_0$  estimate the mean A1C at baseline,  $\beta_4$  estimate the mean change of A1C from baseline to one-year visit;

$B_i = (b_i, \dots, b_i)'$  is the random effect vector for the  $i$ th site;

$B_{ij} = (b_{ij}, \dots, b_{ij})'$  is the random effect vector for the  $j$ th subject in the  $i$ th site;

$\varepsilon_{ij} = (\varepsilon_{ij1}, \dots, \varepsilon_{ij5})'$  is the random error term;

“The mean of baseline A1C measurement is estimated by  $\beta_0$ , mean of 3-month A1C measurement estimated by  $\beta_0 + \beta_1$ , ..., mean of 12-month A1C measurement estimated by  $\beta_0 + \beta_4$ , i.e.,  $\beta_4$  estimate the mean change of A1C from baseline to one-year visit; the 97.5% upper confidence interval of  $\beta_4$  will be calculated and compared the 0.4% non-inferiority margin.”

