### 7.1.3.2. Sensitivity Analysis

Sensitivity analysis will be performed on the ITT population with multiple imputations. The missing data in A1C measurements will be handled by the multiple imputation approach using imputation regression method, where the independent variables in the regression model are age, gender, baseline A1C and BMI. In each imputed dataset, the missing A1C data will be imputed by  $\hat{y} + z\hat{\sigma}$ , where  $\hat{y}$  is the predicted value from regression,  $Z$  is a standard normal random variable,  $\hat{\sigma}$  is the estimated standard deviation of the random residual from the regression model. The imputation

will be performed five times using the MI procedure and the analysis results will be combined to form one inference using the MIANALYZE procedure in SAS 9.3.

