### 7.1.3.3. Descriptive Statistics

The primary endpoint will also be summarized (descriptive statistics) and stratified by:

- Investigational Site
- Age
  - Adults age 22 and older
  - Adolescents age 16-21
- Ethnicity
  - Hispanic/Latino
  - Non-Hispanic/Non-Latino
  - Subject refused
- Race
  - American Indian/Alaska Native
  - Black/African-American
  - White - anticipated maximum less than 80%
  - Native Hawaiian/Other Pacific Islander
  - Asian
  - Other
  - Subject refused
- Baseline BMI according to WHO criteria [World Health Organization, 2011]
  - Underweight subjects (BMI less than 18.5 kg/m^2)
  - Normal weight subjects (BMI 18.5 to 24.99 kg/m^2):
  - Overweight subjects (BMI 25.00 to 29.99 kg/m^2)
  - Obese subjects (BMI 30.00 to 39.99 kg/m^2)
  - Morbidly obese subjects (BMI greater than or equal to 40 kg/m^2)
- Gender
  - Male
  - Female
- Diabetes Classification
  - Diabetes type 1
  - Diabetes type 2
  - Other diagnosis of Diabetes
- Duration of Diabetes
  - Duration of diabetes less than 20 years
  - Duration of diabetes greater than or equal to 20 years
- Hypoglycemic Unawareness Questionnaire
  - Patients with intact hypoglycemic awareness (95% confidence interval will be provided)

- Patients who have impaired hypoglycemic awareness (95% confidence interval will be provided)
- Transition Groups
  - Subjects who have been exposed to the 530G pump therapy with the TS feature ON for 7 days or less prior to screening
  - Subjects who have been exposed to the 530G pump therapy with the TS feature ON for 8 to 365 days prior to screening

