7.2 General Methodology

7.2.1 Primary Efficacy Analysis

A mixed effects model will be used to produce the estimate and confidence interval of the overall mean change in A1C while accounting for inter-site variability: The 97.5% upper confidence interval of A1C will be calculated and compared to the 0.4% non-inferiority margin with the CEP 266 study population. As for endpoint analysis, the proposed mixed effects model using all A1C measurements has more power than the model only using Change in A1C from baseline to one-year visit.

$$Y_{ij} = X_{ij}\beta + B_i + B_{ij} + \varepsilon_{ij}$$

where

$Y_{ij} = (Y_{ij1}, \dots, Y_{ij5})'$ is the A1C measurement vector for the jth subject in the ith site;

$$X_{ij} = \begin{pmatrix} 1 & 0 & 0 & 0 & 0 \\ 1 & 1 & 0 & 0 & 0 \\ 1 & 0 & 1 & 0 & 0 \\ 1 & 0 & 0 & 1 & 0 \\ 1 & 0 & 0 & 0 & 1 \end{pmatrix}$$

is a the covariate vector for the jth subject in the ith site;

$$\beta = \begin{pmatrix} \beta_0 \\ \beta_1 \\ \beta_2 \\ \beta_3 \\ \beta_4 \end{pmatrix}$$

is the coefficient vector, β_0 estimate the mean A1C at baseline, β_4 estimate the mean change of A1C from baseline to one-year visit;

$B_i = (b_{i1}, \dots, b_{i5})'$ is the random effect vector for the ith site;

$B_{ij} = (b_{ij1}, \dots, b_{ij5})'$ is the random effect vector for the jth subject in the ith site;

$\varepsilon_{ij} = (\varepsilon_{ij1}, \dots, \varepsilon_{ij5})'$ is the random error term;

“The mean of baseline A1C measurement is estimated by β_0 , mean of 3-month A1C measurement estimated by $\beta_0 + \beta_1$, ..., mean of 12-month A1C measurement estimated by $\beta_0 + \beta_4$, i.e., β_4 estimate the mean change of A1C from baseline to one-year visit; the 97.5% upper confidence interval of β_4 will be calculated and compared the 0.4% non-inferiority margin.”

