7.3 Center Pooling

Data will be pooled for analysis.

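### The primary A1C model in Protocol 7.1.3.1 leaves between-site variation in change out of the limit tested against 0.4%; the SAP prints a different model, and neither states a covariance

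*Protocol*

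**What the plan says.** Protocol 7.1.3.1 and SAP 7.2.1 both model the five A1C values of subject j at site i as Y = Xβ + B_i + B_ij + ε. The tested parameter is β4, month 12 minus baseline. Non-inferiority is declared if its one-sided 97.5% upper limit is below 0.4%. The protocol says the model will "produce the estimate and confidence interval of the overall mean change in A1C while accounting for inter-site variability".

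The printed random effects differ:

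- **Protocol 7.1.3.1:** B_i = (b_i, …, b_i)′ and B_ij = (b_ij, …, b_ij)′, one value per site and one per subject, the same at every visit.
- **SAP 7.2.1:** B_i = (b_i1, …, b_i5)′ and B_ij = (b_ij1, …, b_ij5)′, a separate value at each visit. The first "is the random effect vector for the ith site".

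Neither gives a covariance for these effects. Of ε the SAP says only that it "is the random error term", and the protocol adds nothing. On sites, SAP 7.3 says "Data will be pooled for analysis". Protocol 7.1.3.3 lists investigational site first among the factors for a descriptive summary of the primary endpoint. SAP section 3 makes the SAP the governing text for the final report.

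**The concern.** The protocol promises a confidence interval for change that allows for differences between sites. A site intercept allows for differences in A1C level. If sites also differ in how A1C changes over the year, that variation belongs in the standard error of β4, and the protocol's formula has no term for it.

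The missing error covariance raises a second question. A subject intercept with independent, equal-variance errors forces every pair of visits to be equally correlated. If visits 12 months apart are less correlated than visits 3 months apart, that model understates the variance of the 12-month change.

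The non-inferiority decision is a single upper limit against a single margin. From the current text, two competent analysts could fit different models and report different limits. Both omissions would make the limit too low, which favours a finding of non-inferiority.

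**Working it through.** **Inputs from the documents.** Margin 0.4%, one-sided 0.025, planned true change 0, SD of change 1% (Protocol 7.1.1.1, SAP 6.1); 426 enrolled and 40 centres activated (Protocol 6.1, SAP 5.2).

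**Assumed.** 320 completers (Protocol 11.1 counts enrolment at consent, so 426 includes screen failures and dropouts); 40, 30 or 25 equal-sized contributing sites (activated does not mean enrolling); the site ICC of change; the AR(1) decay per visit.

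**1. The plan's own figure.** With 100 subjects, power = Φ(0.4 × √100 / 1 − 1.96) = Φ(2.04) = 97.9%, or 97.7% by the noncentral t. The stated power of over 95% reproduces.

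**2. Cancellation.** Under the protocol's formula, for each subject:

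Y_ij5 − Y_ij1 = β4 + (b_i − b_i) + (b_ij − b_ij) + (ε_ij5 − ε_ij1).

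Both random effects drop out. With complete data the estimate of β4 is exactly the mean paired change. A generalised least squares fit (426 subjects, 40 sites, SD of change 1%) gave SE 0.0485 = 1/√426 at site variances of 0, 0.16, 1 and 4, with equal and with unequal sites. Under the SAP's formula read literally, b_i5 − b_i1 remains, so site variation in change would enter. However, the visit-indexed subject vector then cannot be separated from ε without a stated covariance.

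**3. Site variation in change.** Model SE = 1/√320 = 0.0559. Design effect DE = 1 + (320/G − 1) × ICC. Error at a true change of 0.40% = P(Z > 1.96/√DE).

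| Sites G | ICC | DE | One-sided error |
|---|---|---|---|
| 40 | 0.02 | 1.14 | 3.3% |
| 40 | 0.05 | 1.35 | 4.6% |
| 30 | 0.05 | 1.48 | 5.4% |
| 25 | 0.05 | 1.59 | 6.0% |

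A separate simulation (426 subjects, 40 sites, 4,000 trials) gave 2.5%, 3.0%, 4.4% and 8.2% for a between-site SD of change of 0, 0.1, 0.2 and 0.3%. An analysis of site means stayed at 2.3% to 2.7%.

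**4. Independent errors fitted to decaying correlation.** The intercept model estimates the variance of change from the average correlation over all ten visit pairs; the true variance uses the baseline to month-12 pair. SE ratio = √[(1 − mean ρ)/(1 − ρ⁴)], where mean ρ = (4ρ + 3ρ² + 2ρ³ + ρ⁴)/10. Error = P(Z > 1.96 × ratio).

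| ρ | mean ρ | ratio | One-sided error |
|---|---|---|---|
| 0.3 | 0.153 | 0.924 | 3.5% |
| 0.5 | 0.306 | 0.860 | 4.6% |
| 0.9 | 0.814 | 0.735 | 7.5% |

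**5. Which estimates would be decided differently.** The largest passing estimate is 0.4 minus critical value × SE.

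- Intercept model with independent errors: 0.299, 0.306, 0.320% at decay 0.3, 0.5, 0.9.
- Paired SE: 0.4 − 1.96 × 0.0559 = 0.290%.
- Clustered SE, t with G − 1 df, 40 sites: 0.279% (ICC 0.02) and 0.269% (ICC 0.05).
- Clustered SE, ICC 0.05, fewer sites: 0.4 − 2.045 × 0.0681 = 0.261% (30 sites) and 0.4 − 2.064 × 0.0705 = 0.255% (25 sites).

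At an estimate of 0 the upper limit runs from 1.96 × 0.0411 = 0.08% to 2.064 × 0.0705 = 0.15%, far below 0.4% in every case.

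**6. Under multiple imputation.** SAP 7.4 names the imputed ITT population as primary, whereas SAP 7.1.3.3 names completed cases. A simulation of the planned imputation (assumed 400 subjects with baseline at 40 sites, 20% without month 12, five imputations) gave these errors with the intercept-model SE: 2.0% with neither problem, 3.1% and 5.0% at decay 0.5 and 0.9, and 4.5% at ICC 0.05. Monte Carlo error is about 0.2 to 0.3 points.

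**The case against.** The strongest reply is that the protocol's formula may not be the one used. The SAP governs the report and prints visit-indexed effects, under which the cancellation fails. If that difference is only an artefact of PDF reading, the mismatch disappears. This stands as a limit on the claim. Either way something remains: with intercepts, site variation in change is missing; with visit-indexed effects, the model cannot be fitted as written. The covariance is absent in both.

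It is also fair that the decay problem is conditional. Neither document says errors will be independent, and if another structure is intended this part is only missing detail. The exact cancellation needs complete A1C data, and the completer definition, "The Completed Cases (CC) population is all subjects who complete the trial", does not guarantee that every value is present.

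Four stronger readings are tempting but not supported:

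- A reader might infer that the limit reflects site differences in A1C level. With complete data it reflects differences in neither level nor change.
- A reader might call the sentence that "the proposed mixed effects model using all A1C measurements has more power than the model only using Change in A1C from baseline to one-year visit" an error. With complete data and independent errors the gain is very small (97.88% against 97.73% at 100 subjects) but in the stated direction, and it does not affect the decision.
- A reader might want the imputation model changed, "where the independent variables in the regression model are age, gender, baseline A1C and BMI". In simulation with a site-clustered SE, adding the other A1C visits gave errors of 2.1, 2.1, 2.6 and 3.0%, against 2.1, 2.0, 2.3 and 2.9% without them, so there was no gain.
- A reader might compound the widening from decay and from clustering. That needs both assumptions at once, and the documents give no basis for either value.

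**Conclusion.** The point holds as a specification gap in the primary analysis. The protocol states a property, allowance for inter-site variability in the interval for change, that its printed formula does not deliver with complete data. The governing SAP prints a different formula, and the covariance is unstated in both.

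The size is modest and rests on the assumed completers, contributing sites, ICC and decay. One-sided error at the margin rises from 2.5% to between 3.3% and 7.5% when one of the two assumptions holds, and stays at 2.5% when neither does.

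A reader might infer that the trial's conclusion is in doubt. The documents do not support that: at the planned true change of 0 the result is the same under every version. Only an estimate of about 0.26% to 0.32% would be decided differently. This is worth correcting but is not a fatal flaw.

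**What to change.** Print one formula in both documents, for example:

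> A1C at the five visits will be modelled with fixed visit effects and an unstructured 5×5 within-subject covariance, with no separate subject intercept. Site variation in the 12-month change will enter the standard error of β4, through either a random site effect on the change or a site-clustered standard error with a small-sample correction, counting only sites that contribute subjects. The same analysis will be run in each imputed dataset.

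The sponsor should choose one of the two site options in advance. For the clustered option, the bias-reduced (CR2) correction with Satterthwaite degrees of freedom held the error at 2.4% to 2.7% in simulation (40,000 replicates, ICC 0 to 0.05, equal to very uneven sites). If the SAP's visit-indexed effects are intended, state their covariance and correct the protocol to match.

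**Cost.** A few lines of text and code, and a somewhat wider limit. The SE rises by up to about 36% for decay of 0.9 alone (1/0.735), or by 16%, 22% and 26% for a site ICC of 0.05 alone with 40, 30 and 25 sites (√1.35, √1.48, √1.59). The chance of passing stays above 99.9% at a true change of 0. At a true change of 0.2% it falls from 97% to 95% (decay 0.5) or from 92% to 85% (ICC 0.05, 40 sites).
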